7.3 Discontinuation of Therapy and Withdrawal of the Patients from the Study

Study therapy should be discontinued and the patient should be withdrawn from the study due to any of the following reasons:

- Informed consent withdrawal (the patient has made the decision to stop the participation in study for any reason)
- The patients require other antibiotic treatment
- Development of any adverse event, including serious adverse event, clinical significant deviation in the laboratory results, or concomitant disease, which at the investigator's opinion indicates, that continuation of the study medication administration is not at the patient's best interest
- Pregnancy
- Termination of the study by the Sponsor (e.g. in case of poor safety results)
- Termination of the study by the Regulatory Authority (e.g. in case of poor safety results).

CONFIDENTIAL Page 36 of 88

In all cases the reason of termination of participation in study must be recorded in eCRF. When the patient is withdrawn from the study, all efforts should be made to perform all procedures scheduled for the "early termination visit":

- if the "early termination visit" coincides in time with scheduled visit the procedures of that visit should be done (Section 9.2);
- if the "early termination visit" coincides in time with unscheduled visit the minimum number of procedures should comply with the "End of treatment visit" (Section 9.2.3).

All the patients withdrawn from the study will receive treatment in accordance with the standards adopted in the hospital.

Withdrawn patients will not be replaced.

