8.7.2 Prohibited and limited in use therapy

During treatment period (from Visit 1 to Visit 3) the following medications should be prohibited:

- 1. Antacids, multivitamins containing calcium, magnesium, iron, zinc, or aluminum, and sucralfate should be prohibited within 3 hours before and after oral administration of the investigational drug. Intravenous therapy should not be coadministered with any solution containing multivalent cations, e.g., magnesium, through the same intravenous line.
- 2. Probenecid.

During study period (from Visit 1 to Visit 5) the following medications should be prohibited:

- 1. Drugs that may prolong the QT interval with known risk or possible risk of Torsades de Pointes (TdP). The list of these drugs is presented in Appendix 3.
- 2. Chemotherapeutic agents or antitumor drugs.
- 3. Other systemic antibacterial drugs (except for treatment failure).
- 4. Systemic immunosuppressive drugs, including inhaled steroids.
- 5. Drugs that may act to alter the signs and symptoms of infections (e.g., antipyretics, analgesics, antihistamines, or cough suppressants) since day 3 (including) of the treatment.
- 6. Investigational products other than studied in this trial and other than the patient has been randomized.

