10.2.2 Clinical response assessment

The investigator will evaluate clinical response to treatment on Day 4(8) of the study (at Visit 2, switch from intravenous to oral therapy), within 1-2 days (Visit 3, end of treatment) and within 7-9 days (Visit 4, test of cure) after the last dose. Criteria for evaluation of clinical response to the therapy are presented in Table 10-1.

Table 10-1 Criteria for evaluation of clinical response

Category	Criteria
Clinical success	 All signs and symptoms of pneumonia presented at Visit 1 (Day 1) are resolved (i.g., resolution of fever, absence of intoxication, purulent sputum, and respiratory insufficiency) or improved with no worsening or appearance of new signs and symptoms of pneumonia. There is no requirement for additional antibiotic therapy. Chest roentgenograms (CT scans) are cured or improved (only for TOC visit).
Clinical failure	 Persistence or worsening in signs and symptoms of the acute process with either failure to show improvement in the clinical findings, initial improvement in signs and symptoms followed by clinically significant worsening before the assessment. Additional antimicrobial therapy required.

CONFIDENTIAL Page 53 of 88

	 Progression (worsening) of chest roentgenogram (CT scans) abnormalities or unchanged chest roentgenogram features (only for TOC visit).
	 Death because of pneumonia.
Indeterminate	• No evaluation possible: the patient was lost to follow-up, or died
	because of noninfectious-related reasons or infection other than
	pneumonia (as judged by the investigator).

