12 STATISTICAL METHODS

12.1 Analysis populations

The following populations will be identified for the statistical analyses:

- Randomized Population (RP): All subjects who were screened and randomized
- Intent-to-Treat Population (ITT): All subjects in the RT population who received at least one complete dose of the drug (Nemonoxacin or Tavanic[®])
- Modified Intent-to-Treat (mITT): Subjects in the ITT population who met the minimal disease criteria (inclusion criteria 3 and 4), and was evaluated for clinical efficacy at least once
- Clinically Evaluable (CE): Per-Protocol subjects in the mITT population (i.e. patients without protocol violations and without a clinical response of "Indeterminate" in the mITT population)
- Bacteriological mITT (b-mITT): Subjects in the mITT population whose bacterial culture yielded at least one baseline bacterial isolate
- Bacteriologically Evaluable (BE): patients in the CE population who had at least one baseline bacterial isolate
- Safety Population (SP): All subjects who received at least one complete dose of the study drug (Nemonoxacin or Tavanic®) and underwent at least one safety evaluation would be included in this data population for safety analysis
- Pharmacokinetic population (PK-C): All subjects who were included in PK study and who had at least 1 measured concentration value.

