12.2 Exclusion of Patients from Analysis

The investigator should not implement any deviation, except where necessary to eliminate an immediate hazard to the patient.

Data obtained from patients with protocol violations/deviations will be included into the efficacy analysis of the modified Intent-to-Treat (mITT) and bacteriological mITT (b-mITT) populations and the safety analysis (safety population, SP) (see Section 12.1). Data obtained from patients with protocol violations and major deviation will not be included into the efficacy analysis of the clinically evaluable (CE) and bacteriologically evaluable (BE) populations (see Section 12.1); however, data obtained from patients with minor deviations may be included into the efficacy analysis of the CE and BE population.

CONFIDENTIAL Page 63 of 88

Any protocol deviations should be documented in the eCRF.

A protocol deviation is any change, divergence, or departure from the study design or procedures of a protocol that is under the investigator's control and that has not been approved by the IEC. Protocol deviations do not interfere with or may not influence significantly the trustworthiness of the obtained data and the results of the clinical study. There are major and minor protocol deviations. Major protocol deviations may lead to quality depreciation of the data for the following analysis (e.g., intake of prohibited medication, skipping TOC visit, etc.). Minor protocol deviations may decrease the data quality, but it is possible to include them in the analysis in CE and BE population (e.g., partial performance of some study procedures, etc.).

A protocol violation is a deviation from the IEC approved protocol that may affect the subject's rights, safety, or well-being and/or the completeness, accuracy and reliability of the study data. The protocol deviation should be referred to violation in the following cases:

- enrollment of patients not eligible according to the inclusion/exclusion criteria,
- enrollment of patients after the Sponsor's announcement about the enrollment termination,
- Poor compliance:
 - Patient took IMPs <80% or >120% predefined total dose (any incomplete intravenous infusion regimen will be recorded as missing 1 dose of drug), or
 - The patient took IMPs <7 days
- Patients who received the treatment different from the one they were randomized to,
- Other deviations that might affect the primary outcome assessment.

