12.6.2 Primary efficacy analysis

The percentage and the number of patients with different categories of clinical response ("clinical success", "clinical failure", "indeterminate") will be summarized by treatment group in mITT and CE populations for Visit 2 (switch to oral therapy), Visit 3 and Visit 4.

The percentage of patients with clinical success (as judged by the investigator) at the test of cure Visit 4 is defined as primary endpoint variable.

In regards to efficacy for CAP, non-inferiority of Nemonoxacin compared to Tavanic[®] will be evaluated for clinical response by using a one-sided 95% confidence interval for the difference in the primary efficacy endpoint (investigational drug minus comparator). Non-inferiority of Nemonoxacin will be stated if the lower boundary of the estimated one-sided 95% confidence interval for the difference in the clinical success rate of Nemonoxacin and Tavanic[®] is above -15% the Farrington-Manning test.

CONFIDENTIAL Page 65 of 88

The primary analysis will be performed in the mITT population.

If non-inferiority is shown, a test on superiority will be performed in addition using the two-sided 95% confidence interval. The test on superiority is significant, if the lower two-sided 95% confidence interval limit is above "0".

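### As listed, the under-7-days rule in 12.2 removes early treatment failures from the supportive CE and BE analyses because of their outcome; the protocol should say whether that is meant

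*Combined protocol and SAP*

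**What the plan says.** Section 12.1 defines CE as the per-protocol part of mITT ("i.e. patients without protocol violations and without a clinical response of" Indeterminate), and BE as CE patients with a baseline isolate. Anyone who leaves CE therefore leaves BE.

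Section 12.2 keeps patients with violations or major deviations out of the CE and BE efficacy analyses. Under its poor-compliance item it lists two grounds: total dose outside 80% to 120% of the predefined amount, and "The patient took IMPs <7 days". Neither refers to the reason for stopping. Its examples of major deviations are "intake of prohibited medication, skipping TOC visit".

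Section 7.3 gives "The patients require other antibiotic treatment" as a reason for which study therapy is discontinued and the patient withdrawn. Table 10-1 in 10.2.2 lists "Additional antimicrobial therapy required" among the criteria for clinical failure; death from pneumonia is another. Section 8.7.2 prohibits "Other systemic antibacterial drugs (except for treatment failure"), so the antibiotic given for failure is exempted there.

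On the choice of set, 12.6.2 states: "The primary analysis will be performed in the mITT population". Section 12.6.3 makes the CE analysis of the same endpoint supportive, by the same method.

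**The concern.** A patient who fails on Day 5 and is moved to another antibiotic has followed 7.3, is a clinical failure by Table 10-1, and has taken study drug for fewer than 7 days. The event that makes the patient a failure also produces the short exposure. If 12.2 is applied to dosing dates as it stands, the patient disappears from CE and BE, whereas a patient who succeeds on a full course stays.

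The CE analysis is there to show whether the mITT result holds in patients treated as planned. A set that loses failures because they failed overstates success in both arms, and its between-arm difference can drift from the mITT difference. Agreement between the two would then be weak corroboration, and disagreement would be hard to interpret. Two competent teams could also build different CE sets from the present text.

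**Working it through.** **Does the rule reach early failures?** Set side by side, the sections give this chain:

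1. Another antibiotic is needed, so study drug stops and the patient is withdrawn (7.3).
2. The same need is clinical failure (Table 10-1).
3. If it arises before 7 days of drug, the listed violation is met (12.2). The under-80% ground can act in the same way if the predefined total dose means the full planned course.
4. The violation removes the patient from CE and hence from BE (12.1, 12.2).

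The effect is plainest at Visit 2, which 12.6.3 also analyses in CE. A patient judged a failure on Days 4 to 7 and stopped before a seventh day of drug necessarily has under 7 days. Failures first seen at Visit 4, for example on the chest film, are untouched.

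**How large could it be?** The plan has no figure on this point to reproduce. From 12.10 come the 82% success rate in both arms, the 15-point margin and about 137 mITT patients per arm. The share f of clinical failures that the rule drops is not in the documents. It is below 1; I show 10%, 25% and 50% as assumptions. With p the mITT success rate and i the Indeterminate share (out of CE on either reading):

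CE rate = p / [p + (1 − p − i)(1 − f)]

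For example, p = 0.82, i = 0, f = 0.25 gives 0.82 / (0.82 + 0.18 × 0.75) = 0.82 / 0.955 = 85.9%.

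With i = 0 and the same f in both arms (differences taken before rounding):

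| f | CE rate if p = 82% | CE rate if p = 67% | Difference, 82 vs 82 | Difference, 67 vs 82 |
|---|---|---|---|---|
| 0 | 82.0% | 67.0% | 0 | -15.0 |
| 10% | 83.5% | 69.3% | 0 | -14.2 |
| 25% | 85.9% | 73.0% | 0 | -12.8 |
| 50% | 90.1% | 80.2% | 0 | -9.9 |

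The 67% is 82% less the 15-point margin.

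With unequal f (test / control), i = 0:

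- 82 vs 82: 10%/25% gives -2.4 points and 25%/50% gives -4.2; reversed, +2.4 and +4.2.
- 67 vs 82: 25%/50% gives 73.0 − 90.1 = -17.1; 50%/25% gives 80.2 − 85.9 = -5.6.

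Sensitivity with i = 5% in each arm (assumed): 67 vs 82 starts at 70.5 − 86.3 = -15.8 and becomes -14.8, -13.2 or -9.9 with equal f. At 82 vs 82 it stays at 0 with equal f and is -3.3 or +3.3 with 25%/50% or 50%/25%.

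**What could it do to the bound?** Take assumed counts of 99/137 (72.3%) against 112/137 (81.8%). With all failures kept, the difference is -9.5 points and the Farrington-Manning one-sided 95% lower bound is -17.8. Dropping 10 of 38 and 6 of 25 failures gives 99/127 against 112/131: difference -7.5, bound -15.5. Dropping 19 of 38 and 12 of 25 gives 99/118 against 112/125: difference -5.7, bound -13.1. In the last case CE would clear -15% although mITT had missed it.

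**The case against.** The strongest reply is that 12.2 never meant these patients. It treats a violation as a kind of deviation, and a deviation is a departure from the protocol "that is under the investigator's control and that has not been approved by the IEC". A stop that 7.3 itself requires is arguably no departure, whoever controls it, and hardly poor compliance. Section 8.7.2 points the same way by allowing antibiotics for failure. This reading is plausible, and may be the intended one. But 12.2 still lists under 7 days without qualification, no section says that such failures stay in CE, and 8.7.2 shows that an exemption was written where one was wanted. Sections 12.5 and 12.9 leave detail to a SAP that is not in the supplied text and may settle the matter.

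A missed Visit 4 after a required withdrawal is only arguably a skipped one, since 7.3 provides an early termination visit. That part is a clarification, not a second defect.

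It is also fair that every non-zero difference above needs either unequal shares or a real deficit in the test arm, and that mITT and b-mITT results will stand beside CE and BE, so a divergence would be visible.

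A reader might infer that the non-inferiority conclusion or its type I error is compromised. The documents do not support this: the decision rests on mITT, 12.2 keeps violations in mITT, and nothing requires CE to pass. Nor does mITT hold every early failure. Section 12.1 requires at least one efficacy evaluation, so a patient never evaluated is already outside mITT, CE and BE, whatever this rule says.

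**Conclusion.** The point holds as a gap in the definition of the supportive sets. As listed, 12.2 excludes early failures from CE and BE because they failed; whether that is intended cannot be decided from the supplied text. Confidence is high that no exemption is written in 12.2, and lower on the size of the effect.

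Under the plan's own assumption of equal success rates, with equal shares dropped, the difference is not biased and only the rates rise. Under a true 15-point deficit with equal shares, the CE difference looks 0.8 to 5.1 points better than it is (-14.2 to -9.9 against -15.0). Unequal shares can push it either way. These are illustrations on assumed shares, not estimates. Severity is minor to should-fix, confined to the supportive analyses.

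**What to change.** Add one paragraph to 12.2 or the SAP before unblinding:

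- The under-7-days and under-80% grounds do not exclude an mITT patient whose study drug was stopped for clinical failure, need for another antibiotic, or death from pneumonia.
- A Visit 4 not held after such a withdrawal does not count as skipping the test-of-cure visit.
- These patients stay in CE as clinical failures. If failure is carried to later visits, the same rule applies in mITT and CE, because 12.6.3 requires the same method in both.
- In BE, the 12.6.3 response categories apply. Presumed persistence and Unevaluable overlap for a clinical failure without a later culture, so state that presumed persistence takes precedence when there is no material for culture.
- If the sponsor wants a minimum exposure before a failure is evaluable, state it in advance as an analysis-set rule, identical in both arms.

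No new data are needed and no treatment rule changes. The costs are somewhat lower CE and BE success rates than under the rule as listed, and different exposure requirements for failures and non-failures. The second is itself a choice that depends on outcome and should be acknowledged as such. If retention was always intended, the paragraph only records it.

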12.3 Criteria for termination of the study

Not applicable. There are no statistical criteria for termination of the study.

12.4 General considerations

Demographic and clinical characteristics at baseline, medical history, efficacy and safety data will be summarized using descriptive statistics by treatment group and by time point of assessment.

Continuous data will be summarized in terms of the mean, standard deviation (SD), median, 25th and 75th percentile, minimum, maximum and number of observations. In general, categorical and ordinal data will be summarized in terms of the frequency and percentage in each category.

Using explorative methods, both treatment groups will be analysed for homogeneity on the basis of patient's baseline characteristics. Analysis of variance (ANOVA) or Wilcoxon-Mann-Whitney test, as appropriate, will be used to test and compare the continuous demographic and baseline characteristics between treatment

CONFIDENTIAL Page 64 of 88

groups. The Pearson χ^2 (or Fisher's exact test) will be used to perform between-group comparisons on categorical and binominal demographic and baseline data.

Medical history will be coded using the Medical Dictionary for Regulatory Activities (MedDRA) version 17.1. The prior and concomitant medication will be coded using World Health Organization (WHO) Drug Dictionary (version 2013-12-19), including ATC code.

For the primary efficacy endpoint, the non-inferiority hypothesis will be tested at one-sided 0.05 significance level. For other statistical analyses statistical significance will be declared at the 2-sided 0.05-level, unless otherwise specified.

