12.6.3 Secondary efficacy analyses

As a supportive analysis, the primary efficacy endpoint will be analyzed in the CE population using the same method as that used for the primary efficacy analysis.

For secondary efficacy analyses, the clinical success rates of the patients in the mITT and CE populations at Visit 2 (switch to oral therapy) and Visit 3 as well as the number (proportion) of patients who needed other antibiotic treatment (treatment failure) will be analyzed using a two-sided 95% confidence interval (equality test) calculated based on the same statistical test as for the primary analysis.

Additionally, the results of statistical comparison of the clinical success rates using the logistic regression will also be provided.

Time to switch therapy from i.v. to oral therapy will be evaluated using the Kaplan – Meier survival analysis method and compared by log-rank test between treatment groups. The Kaplan-Meier curves will be presented graphically.

Microbiological efficacy endpoints will include microbiological success rates evaluated per each patient and by identified pathogens in b-mITT and BE.

The percentage and the number of patients with microbiological success and failure will be summarized by visit and treatment group. Microbiological success is defined as the assessments of eradication and presumed eradication. Other results of assessments (excluding unevaluable) will be regarded as microbiological failure. The difference between microbiological success rates and its CI will be calculated using the same method as that used for the secondary efficacy endpoints.

The percentage and number of the baseline-identified strains (sputum and blood culture) with microbiological success and failure will be summarized by visit and treatment group. The frequency of each category and sample source (sputum and blood culture) will be presented separately and by treatment group. Microbiological data by identified pathogens will be analyzed descriptively.

Microbiological efficacy evaluation

Based on the results of culture (bacteriological) study the microbiological response will be assessed. Microbiological response is defined as:

- 1. Eradication (admission pathogen[s] is absent),
- 2. Presumed eradication (if no material available for culture because of clinical success)
- 3. Persistence (admission pathogen[s] is present),
- 4. Presumed persistence (no material available for culture for patients with clinical failure),

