12.10 Sample size calculation

The primary efficacy objective is to show that Nemonoxacin is not inferior to Levofloxacin (Tavanic[®]) for the treatment of CAP, on the basis of the primary efficacy endpoint - clinical success at Visit 4 (Test of cure visit) in the mITT population. The sample size calculation for this endpoint is based on assuming a clinical success rate of 82% in the treatment and in the active control group, and an eligibility of 80% of the randomized patients for mITT population. Non-inferiority margin is chosen to be 15% (i.e., δ = -15%), a one-sided significance level α is set at 5%. Then, to achieve power of 80%, the sample size for equal allocation is estimated as 171 randomized patients in each group (342 patients totally) that provides about 137 patients in each group (274 patients totally) in the mITT population.

Presumably screening of 382 patients will allow enrollment and randomization of 342 patients.

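### Non-inferiority is judged at one-sided 5% while superiority on the same difference uses the two-sided 95% interval; the planned size supports one-sided 2.5% with about 89% power

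*Combined protocol and SAP*

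**What the plan says.** The level for the primary test is the same wherever it appears (synopsis, 12.4, 12.6.2 and 12.10).

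- Section 12.4: "For the primary efficacy endpoint, the non-inferiority hypothesis will be tested at one-sided 0.05 significance level". For everything else: "For other statistical analyses statistical significance will be declared at the 2-sided 0.05-level, unless otherwise specified".
- Section 12.6.2 evaluates the primary endpoint "using a one-sided 95% confidence interval for the difference in the primary efficacy endpoint" and claims non-inferiority if the lower bound "is above -15% the Farrington-Manning test".
- The same section then adds: "If non-inferiority is shown, a test on superiority will be performed in addition using the two-sided 95% confidence interval".
- Section 12.6.3 uses two-sided 95% intervals for clinical success at Visits 2 and 3, need for other antibiotics, and microbiological success. It makes one exception: "the primary efficacy endpoint will be analyzed in the CE population using the same method as that used for the primary efficacy analysis". The CE analysis is therefore also at one-sided 5%.
- Section 12.10 repeats that "a one-sided significance level α is set at 5" per cent. With 82% success in both arms, a 15-point margin and 80% power, it arrives at 171 randomized and about 137 mITT patients per arm.

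No section explains why non-inferiority uses 5% on its one side while superiority uses 2.5%.

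**The concern.** Two different lower limits will be computed for one difference. The one-sided 95% limit, which is also the lower end of a two-sided 90% interval, decides non-inferiority. The lower end of the two-sided 95% interval decides superiority. The second is always lower, so there is a band of results in which the trial succeeds on the first limit while the second, required by the next step of the same section, lies below -15%. A report with the two limits on opposite sides of the margin is hard to defend.

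The level also fixes how often a drug that is truly 15 points worse would be called non-inferior: about 1 in 20 now, against about 1 in 40 at one-sided 2.5%.

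**Working it through.** **Inputs.** From 12.10: success 82% in both arms, margin 15 points, one-sided 5%, 80% power, 80% of randomized patients in mITT, 171 randomized per arm (171 × 0.80 = 136.8, about 137). From 12.6.2: the Farrington-Manning test.

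**1. The plan's own sample size.** With unpooled variance,

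n = (z_α + z_β)² × 2p(1 − p) / margin² = (1.645 + 0.842)² × 2(0.82)(0.18) / 0.15² ≈ 81.1, so 82 mITT per arm. Dividing by 0.80 gives 103 randomized.

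The Farrington-Manning formula uses success rates restricted to a difference of -15 points (72.3% and 87.3%). Its null SD is 0.557 and the alternative SD is 0.543:

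n = [(1.645 × 0.557 + 0.842 × 0.543) / 0.15]² ≈ 84 mITT, or 105 randomized.

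A continuity correction raises the unpooled figure only to 95 (119 randomized). The stated 137 and 171 are not reproduced.

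**2. Power at the planned 137 per arm, 82% in both arms.** The asymptotic Farrington-Manning power is Φ[(0.15 × √137 − z_α × 0.557) / 0.543]. The exact figure sums binomial probabilities over all outcomes that the test rejects.

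| Level | Asymptotic | Exact | Unpooled Wald |
|---|---|---|---|
| One-sided 5% | 93.9% | 94.1% | 94.4% |
| One-sided 2.5% | 88.9% | 89.4% | 89.8% |

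For 80% power at one-sided 2.5%, 103 (unpooled) or 107 (Farrington-Manning) mITT per arm would be enough.

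**3. Error at the margin.** Exact probability of declaring non-inferiority when the true rates are 67% and 82%, 137 per arm: 5.1% at nominal 5%, 2.5% at nominal 2.5%. At 72% against 82%, it is 26% and 17%.

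**4. Results on which the two limits disagree.** Take 112/137 successes on Tavanic (81.8%). The statistic is z = (difference + 0.15) / restricted standard error. The lower limits come from inverting the same test at 1.645 and 1.960.

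| Nemonoxacin | Difference | z | One-sided 95% limit | Two-sided 95% lower limit |
|---|---|---|---|---|
| 103/137 | -6.6 points | 1.70 | -14.7% | -16.3% |
| 104/137 | -5.8 points | 1.85 | -14.0% | -15.5% |

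Both pass at 1.645 and fail at 1.960. With 102 successes the test fails at both levels (z = 1.54); with 105 it passes at both (z = 2.01). In Wald terms, the observed difference needed moves from about -7.4 to about -5.9 points.

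**5. Sensitivity of power at 137 per arm (exact).** The true rates below are our assumptions.

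| Nemonoxacin v Tavanic | One-sided 5% | One-sided 2.5% |
|---|---|---|
| 82% v 82% (plan) | 94.1% | 89.4% |
| 75% v 75% | 89.1% | 82.0% |
| 70% v 70% | 86.1% | 77.5% |
| 80% v 82% | 86.1% | 78.0% |
| 79% v 82% | 80.3% | 70.6% |

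With fewer evaluable patients and 82% in both arms, power at one-sided 2.5% is 85.1% (120 per arm) or 81.1% (107 per arm).

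**The case against.** The strongest reply is that this is a design choice openly made. The 5% level is prespecified, is stated identically in four places, and is the level named in the sample size section. Testing non-inferiority at one-sided 5% and then superiority at 2.5% per side is a valid ordered sequence and does not raise the error on the primary endpoint above 5%. Nothing in the documents requires one-sided 2.5%. All of this stands.

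Four stronger readings are tempting, and the documents do not support them.

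- A reader might infer that the plan contradicts itself on the level. It does not: section 12.4 sets the two levels side by side.
- A reader might infer that every secondary test uses the stricter level. The CE analysis in 12.6.3 does not, and safety is descriptive only (12.7).
- A reader might infer that the primary claim has the loosest error control in the protocol. Only the per-side rate is higher. Each two-sided secondary test also carries 5% in total, and 12.4 and 12.6.3 state no multiplicity adjustment for them, so as a set they are less well controlled.
- A reader might infer that 171 was derived for one-sided 2.5% and 90% power, since the unpooled formula then gives 138 mITT and 173 randomized per arm. The closeness is real, but the documents do not say how 171 was reached.

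The objection on power also stands in part. Power stays above 80% at one-sided 2.5% under the plan's assumption of no true difference. With a deficit of 2 or 3 points it falls below 80%, whereas the current rule keeps it at 80% or above. Finally, whether 15 points is an acceptable margin is a separate question that a change of level does not settle.

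**Conclusion.** The point holds as a worthwhile improvement, not as an error in the plan. The present rule can produce a non-inferiority claim that the two-sided 95% interval for the same difference does not support. The stricter rule would halve the chance of accepting a drug at the margin (5.1% to 2.5%) and reduce power from about 94% to about 89%. That power rests on 82% success in both arms, no true difference, and 137 mITT patients per arm.

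Separately, the 80% power stated in 12.10 does not follow from its inputs at the planned size, whichever level is kept.

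**What to change.** In the synopsis, 12.4, 12.6.2, 12.6.3 (CE analysis) and 12.10:

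- Declare non-inferiority if the lower limit of the two-sided 95% Farrington-Manning interval for nemonoxacin minus Tavanic is above -15%.
- Use that same interval for the superiority test.
- In 12.10, replace one-sided 5% with one-sided 2.5%, and replace the stated 80% power with about 89% for 137 mITT patients per arm and 82% success in both arms.
- Leave enrolment at 342.

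**Cost.** Changing the primary decision rule is a protocol amendment, needs ethics committee approval (section 13), and must be made before unblinding. It adds no patients, visits or procedures. Under the plan's assumptions it costs about 5 points of power. If nemonoxacin is truly 2 or 3 points lower, the loss is about 8 or 10 points, and the sponsor should accept that knowingly.

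**If the sponsor keeps one-sided 5%,** give the reason in 12.4, and still correct 12.10 to state about 94% power for 137 per arm.
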